## 6.0 TRIAL PROCEDURES

### 6.1 Trial Procedures

The Trial Flow Chart - Section 5.0 summarizes the trial procedures to be performed at each visit. Individual trial procedures are described in detail below. It may be necessary to perform these procedures at unscheduled time points if deemed clinically necessary by the investigator.

Furthermore, additional evaluations/testing may be deemed necessary by the Sponsor and/or Merck for reasons related to participant safety. In some cases, such evaluation/testing may be potentially sensitive in nature (e.g., HIV, Hepatitis C, etc.), and thus local regulations may require that additional informed consent be obtained from the participant. In these cases, such evaluations/testing will be performed in accordance with those regulations.

#### 6.1.1 Informed Consent

Consent must be documented by the participant's dated signature or by the participant's legally acceptable representative's dated signature on a consent form along with the dated signature of the person conducting the consent discussion.

A copy of the signed and dated consent form should be given to the participant before participation in the trial.

The initial informed consent form, any subsequent revised written informed consent form and any written information provided to the participant must receive the IRB/ERC's approval/favorable opinion in advance of use. The participant or his/her legally acceptable representative should be informed in a timely manner if new information becomes available that may be relevant to the participant's willingness to continue participation in the trial. The communication of this information will be provided and documented via a revised consent form or addendum to the original consent form that captures the participant's dated signature or by the participant's legally acceptable representative's dated signature.

Specifics about a trial and the trial population will be added to the consent form template at the protocol level.

The informed consent will adhere to IRB/ERC requirements, applicable laws and regulations and Sponsor requirements.

##### 6.1.1.1 Inclusion/Exclusion Criteria

All inclusion and exclusion criteria will be reviewed by the investigator or qualified designee to ensure that the participant qualifies for the trial.

### **6.1.1.2 Medical History**

A medical history will be obtained by the investigator or qualified designee. Medical history will include all active conditions, and any condition diagnosed within the prior 10 years that are considered to be clinically significant by the Investigator. Details regarding the disease for which the participant has enrolled in this study will be recorded separately and not listed as medical history.

### **6.1.1.3 Prior and Concomitant Medications Review**

#### **6.1.1.3.1 Prior Medications**

The investigator or qualified designee will review prior medication use, including any protocol-specified washout requirement, and record prior medication taken by the participant within 28 days before starting the trial. Treatment for the disease for which the participant has enrolled in this study will be recorded separately and not listed as a prior medication.

#### **6.1.1.3.2 Concomitant Medications**

The investigator or qualified designee will record medication, if any, taken by the participant during the trial. All medications related to reportable SAEs and ECIs should be recorded as defined in Section 6.1.2.1.

### **6.1.1.4 Disease Details and Treatments**

#### **6.1.1.4.1 Disease Details**

The investigator or qualified designee will obtain prior and current details regarding disease status.

#### **6.1.1.4.2 Prior Treatment Details**

The investigator or qualified designee will review all prior cancer treatments including systemic treatments, radiation and surgeries.

#### **6.1.1.4.3 Subsequent Anti-Cancer Therapy Status**

The investigator or qualified designee will review all new anti-neoplastic therapy initiated after the last dose of trial treatment.

### **6.1.1.5 Assignment of Subject Number**

Each subject will be assigned a unique subject identifier.

## 6.1.2 Clinical Procedures/Assessments

### 6.1.2.1 Adverse Event (AE) Monitoring

Complete and timely reporting of adverse events (AEs) is required to ensure the safety of patients. Reporting requirements are determined by the characteristics of the adverse event including the *grade* (severity), the *relationship to the study therapy* (attribution), and the *prior experience* (expectedness) of the adverse event. The guidelines outlined in this section, as well as the specific direction on each report form must be followed. The NCI Common Terminology Criteria for Adverse Events v4.0 (CTCAE) will be used to classify and grade toxicities.

The investigator or qualified designee will assess each participant to evaluate for potential new or worsening AEs as specified in the Trial Flow Chart and more frequently if clinically indicated. Adverse experiences will be graded and recorded throughout the study and during the follow-up period according to NCI CTCAE Version 4.0 (see Appendix 2). Toxicities will be characterized in terms regarding seriousness, causality, toxicity grading, and action taken with regard to trial treatment.

Please refer to section 7.2 for detailed information regarding the assessment and recording of AEs.

### 6.1.2.2 Full Physical Exam

The investigator or qualified designee will perform a complete physical exam during the screening period. Clinically significant abnormal findings should be recorded as medical history. A full physical exam should be performed during screening,

### 6.1.2.3 Directed Physical Exam

For cycles that do not require a full physical exam per the Trial Flow Chart, the investigator or qualified designee will perform a directed physical exam as clinically indicated prior to trial treatment administration.

### 6.1.2.4 Vital Signs

The investigator or qualified designee will take vital signs at screening, prior to the administration of each dose of trial treatment and at treatment discontinuation as specified in the Trial Flow Chart (Section 5.0). Vital signs should include temperature, pulse, respiratory rate, weight and blood pressure. Height will be measured at screening only.

#### **6.1.2.5 Eastern Cooperative Oncology Group (ECOG) Performance Scale**

The investigator or qualified designee will assess ECOG status (see Appendix 1) at screening, prior to the administration of each dose of trial treatment and discontinuation of trial treatment as specified in the Trial Flow Chart.

#### **6.1.2.6 Tumor Imaging and Assessment of Disease**

Tumor imaging consists of standard of care FDG-PET/CT of the chest, abdomen, and pelvis at baseline within 42 days of day 1 of cycle 1. Post therapy (interim PET for those receiving more than 2 total cycles) imaging will consist of FDG-PET/CT of the chest, abdomen, and pelvis and should be performed as early as day 16 of cycle 2, but prior to any additional antineoplastic therapy. Additional imaging studies may be performed at the discretion of the treating provider.

#### **Assessment of Disease**

Definitions of Disease, Criteria for Evaluation and Endpoint Definitions – response will be defined by standard NCI criteria (Lugano 2014) for lymphoid malignancies.

#### **6.1.2.7 Tumor Tissue Collection and Correlative Studies Blood Sampling**

Correlative studies may be carried out whenever possible for ctDNA testing. Blood samples will be collected in two to four 10 mL K2EDTA tubes at baseline, on cycle 2 day 1, and after cycle 2. Additional blood draws can be collected at the investigator's discretion. Additionally, up to 10 unstained slides of diagnostic tissue or tissue block may also be collected.

#### **6.1.3 Laboratory Procedures/Assessments**

Details regarding specific laboratory procedures/assessments to be performed in this trial are provided below.

Laboratory tests for hematology, chemistry, and others are specified in Table 6.

Table 6 Laboratory Tests

Complete blood count (CBC) with differential	Comprehensive metabolic panel	Other
Hematocrit	Albumin	Serum or urine $\beta$ -human chorionic gonadotropin( $\beta$ -hCG)†
Hemoglobin	Alkaline phosphatase	Total triiodothyronine (T3)
Platelet count	Alanine aminotransferase (ALT)	Free tyroxine (T4)
WBC (total and differential)	Aspartate aminotransferase (AST)	Thyroid stimulating hormone (TSH)
Red Blood Cell Count	Lactate dehydrogenase (LDH)	Erythrocyte Sedimentation Rate (ESR)
Absolute Neutrophil Count	Carbon Dioxide ‡	
Absolute Lymphocyte Count	( $CO_2$ or bicarbonate)	
	Uric Acid	
	Calcium	
	Chloride	Blood for correlative studies
	Glucose	
	Sodium	
	Total Bilirubin	
	Direct Bilirubin ( If total bilirubin is elevated above the upper limit of normal )	
	Total protein	
	Blood Urea Nitrogen	

Laboratory tests for screening should be performed within 10 days prior to the first dose of treatment. After Cycle 1, pre-dose laboratory procedures can be conducted up to 72 hours prior to dosing. Results must be reviewed by the investigator or qualified designee and found to be acceptable prior to each dose of trial treatment.

#### **6.1.4 Other Procedures**

##### **6.1.4.1 Withdrawal/Discontinuation/Visit Requirements**

When a subject discontinues/withdraws prior to trial completion, all applicable activities scheduled for the final trial visit should be performed at the time of discontinuation. Any adverse events which are present at the time of discontinuation/withdrawal should be followed in accordance with the safety requirements outlined in Section 6.2 - Assessing and Recording Adverse Events. Visit requirements are outlined in Section 5.0 - Trial Flow Chart. Specific procedure-related details are provided above in Section 6.0 - Trial Procedures.

##### **6.1.4.2 Screening**

###### **6.1.4.2.1 Screening Period**

The screening period begins upon signing consent and prior to Cycle 1 Day 1 of study therapy. The screening period may last up to 42 days, which may be extended provided the patients re-signs a consent form.

###### **6.1.4.3 Treatment Period**

The treatment period includes APVD, administered every 28 days. Administration of study medications may be +/- 2 days of the expected date as outlined in section 2.2. All other procedures should be performed per the Study Flow Chart.

###### **6.1.4.4 Post-Therapy Visit**

Post therapy procedures should be performed per the Study Flow Chart and include Physical Exam, Laboratory assessments, and imaging studies.

###### **6.1.4.5 Safety Follow-Up Visit**

The mandatory Safety Follow-Up Visit should be conducted approximately 30 days after the last dose of study treatment or before the initiation of a new anti-cancer treatment, whichever comes first. All AEs that occur prior to the Safety Follow-Up Visit should be recorded. Participants with an AE of Grade > 1 will be followed until the resolution of the AE to Grade 0-1 or until the beginning of a new anti-cancer therapy, whichever occurs first. SAEs that occur within 90 days of the end of treatment or before initiation of a new anti-cancer treatment should also be followed and recorded. \

#### **6.1.4.6 Follow-up Visits**

Follow-up after Cycle 2 (Cycle 6 for part B) will be conducted per Standard of Care. Patients will be tracked for subsequent therapy, response, progression-free, and overall survival up to 5 years.

### **6.2 Assessing and Recording Adverse Events**

Routine reporting is required for all grade 3, 4 and 5 adverse events. Grade 1 or 2 AEs will not be captured or reported with the exception of ANC, platelet nadirs, or immune related adverse events. Routine reports include data after each cycle of therapy and 30 days after the last dose of study drugs, or until the patient receives an alternative anti-cancer therapy, whichever date comes first.

Routine reporting will be conducted in accordance with FHCRC/Cancer Consortium IRB policies, applicable FDA regulations, and agreements with Merck.

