#### **4.2.2 Dose Modification and toxicity management for immune-related AEs associated with pembrolizumab**

AEs associated with pembrolizumab exposure may represent an immunologic etiology. These immune-related AEs (irAEs) may occur shortly after the first dose or several months after the last dose of pembrolizumab treatment and may affect more than one body system simultaneously. Therefore, early recognition and initiation of treatment is critical to reduce complications. Based on existing clinical study data, most irAEs were reversible and could be managed with interruptions of pembrolizumab, administration of corticosteroids and/or other supportive care. For suspected irAEs, ensure adequate evaluation to confirm etiology or exclude other causes. Additional procedures or tests such as bronchoscopy, endoscopy, skin biopsy may be included as part of the evaluation. Based on the severity of irAEs, withhold or permanently discontinue pembrolizumab and administer corticosteroids. Dose modification and toxicity management guidelines for irAEs associated with pembrolizumab are provided in Table 3.

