## 5.0 STUDY FLOW CHART – PART A AND PART B

Required Studies	Pre-Entry (within 4 weeks unless indicated otherwise)	Within 2 days prior to each dose 	Post Therapy 	Safety Follow-up Visit 	Follow-up 
Physical					
History and Physical (H&P)	X	X 	X	X	
Performance Status	X	X 	X	X	
Clinical Disease Assessment	X	X 	X		
Adverse Event Assessment	X	X 	X	X	
Lab					
ESR, TSH, T3, T4, LDH	X 		X 	X	
Complete blood count with differential 	X	X 	X	X	
Comprehensive metabolic panel 	X	X 	X	X	
Pregnancy test	X 				
Radiology					
Left Ventricular Ejection Fraction (LVEF)	X 				
PET/CT	X 		X		
Correlative Studies 	X		X		

1. For Cycle 1 Day 1, pre-entry H&P, performance status, disease assessment and adverse event assessment may be used (these do not need to be repeated within 2 days) and labs done within 10 days are acceptable.
2. Pregnancy test in women of childbearing potential.
3. EF must be  $\geq 50\%$  within 56 days.
4. Post therapy (interim PET for patients planning on receiving more than 2 total cycles) studies should be done as early as day 16 of cycle 2 but prior to any additional antineoplastic therapy unless other objective evidence of progressive disease. For patients who proceed with more than 2 cycles of therapy (Optional part A, mandatory 6 cycles for part B), an additional post therapy visit with additional PET/CT should be performed 28-35 days after the expected last dose of chemotherapy, which may also serve as the post treatment safety visit.
5. A safety follow up visit should be performed 28-35 days after last dose of study therapy is administered. This may be an additional visit depending on the date of the post-therapy visit, but may be combined with the post-therapy visit if the windows overlap.
6. Follow-up after cycle 2 will be standard of care. Patient will be tracked for subsequent therapy, response, progression-free, and overall survival after completion of 2 cycles of therapy up to 5 years.
7. Patients must have an ESR, TSH, T3 and T4 performed within 14 days prior to registration.
8. Dose is defined as a day in which one receives any of the medications outlined in section 4.2
9. See Table 6 for list of components
10. LDH and ESR not required at Post Therapy or Safety follow up visit

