### 6.3.2 Sponsor Responsibility for Reporting Adverse Events

A serious adverse event is any adverse event occurring at any dose or during any use of Merck's product that:

- Results in death;
- Is life threatening;
- Results in persistent or significant disability/incapacity;
- Results in or prolongs an existing inpatient hospitalization;
- Is a congenital anomaly/birth defect;
- Is another important medical event
- **Note:** In addition to the above criteria, adverse events meeting either of the below criteria, although not serious per ICH definition, are reportable to the Merck in the same timeframe as SAEs to meet certain local requirements. Therefore, these events are considered serious by Merck for collection purposes.
  - Is a new cancer (that is not a condition of the study);
  - Is associated with an overdose.

For the time period beginning when the consent form is signed until treatment allocation/randomization, any serious adverse event, or follow up to a serious adverse event, including death due to any cause that occurs to any participant must be reported within 24 hours to the Sponsor and within 2 working days to Merck Global Safety if it causes the participant to be excluded from the trial, or is the result of a protocol-specified intervention, including but not limited to washout or discontinuation of usual therapy, diet, placebo treatment or a procedure.

For the time period beginning at treatment allocation/randomization through 90 days following cessation of treatment, or 30 days following cessation of treatment if the participant initiates new anticancer therapy, whichever is earlier, any serious adverse event, or follow up to a serious adverse event, including death due to any cause whether or not related to the Merck product, must be reported within 24 hours to the Sponsor and within 2 working days to Merck Global Safety.

Additionally, any serious adverse event, considered by an investigator who is a qualified physician to be related to Merck product that is brought to the attention of the investigator at any time following consent through the end of the specified safety follow-up period specified in the paragraph above, or at any time outside of the time period specified in the previous paragraph also must be reported immediately to Merck Global Safety.

All participants with serious adverse events must be followed up for outcome.

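### New immune-related events judged non-serious have no working capture route after about day 30, and the protocol's sections disagree on how long they are recorded

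*Combined protocol and SAP*

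**What the plan says.** Section 6.2 requires routine reporting of Grade 3 to 5 events. For lower grades it makes a deliberate exception: "Grade 1 or 2 AEs will not be captured or reported with the exception of ANC, platelet nadirs, or immune related adverse events". Immune-related events are therefore wanted at every grade. The window is then set: "Routine reports include data after each cycle of therapy and 30 days after the last dose of study drugs". It closes sooner if the patient moves to another cancer treatment.

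Two other sections stop at about the same time. Section 6.1.4.5 says "All AEs that occur prior to the Safety Follow-Up Visit should be recorded" and places that visit at roughly 30 days. Note 5 to the Section 5.0 flow chart says "A safety follow up visit should be performed 28-35 days after last dose of study therapy is administered". The chart shows no adverse-event assessment in its Follow-up column.

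Section 4.2.2 describes the timing of immune-related events differently: they "may occur shortly after the first dose or several months after the last dose of pembrolizumab treatment". Section 6.1.2.1 says that adverse experiences are graded and recorded over the whole study, including the follow-up period.

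Some capture does continue beyond day 30:
- Section 6.3.2 reports serious events "through 90 days following cessation of treatment", shortened to 30 days if new anti-cancer therapy begins. Serious events judged related to pembrolizumab are reported whenever they come to light.
- Section 6.3.1.1 applies the same 90-day window to events of clinical interest.
- Section 6.1.4.5 follows events already open: "Participants with an AE of Grade > 1 will be followed until the resolution of the AE to Grade 0-1", or until new therapy starts.

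**The concern.** Pembrolizumab is the drug added to AVD, and immune-related events are its characteristic toxicity. The plan marks these events for capture at all grades and says they can begin months after the last dose. It nevertheless applies to them the same 30-day routine window as to any chemotherapy toxicity. Starting other therapy can close that window earlier still.

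Two things are at stake. The first is completeness: the trial's hypothesis in Section 3.1 is that the combination is safe, and Section 3.5.1 suggests it may be better tolerated. An account of immune toxicity that thins out after day 30 supports those statements only in part. The second is consistency: staff who follow Section 6.1.2.1 would record a late thyroid event, while staff who follow Section 6.2 or the flow chart would not.

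**Working it through.** The plan gives no figure to reproduce on this point. The check compares the recording rules and then places the windows on the calendar.

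**Step 1. What happens to an event after about day 30**

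| Type of event | Route | Limit |
|---|---|---|
| New, serious, including events judged medically important (Table 7, Section 6.3.2) | Serious-event reporting | 90 days, or 30 if new therapy starts; no limit if judged related |
| New, on the clinical-interest list (Section 6.3.1.1): overdose without effects, or one combined AST/ALT, bilirubin and alkaline phosphatase pattern | Clinical-interest reporting | 90 days, or 30 if new therapy starts |
| Above Grade 1 and already open at the safety visit (Section 6.1.4.5) | Followed | Until Grade 0-1 or new therapy |
| New, immune-related, judged non-serious, not on the list | Only the general sentence in Section 6.1.2.1 | No scheduled assessment or reporting window behind it |

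Only the last row is uncovered. Grade 2 hypothyroidism that begins after the safety visit is an example. Other data do not fill the gap. Section 4.3.1 limits concomitant medication after 30 days to serious and clinical-interest events, so treatment given for such an event would not be recorded either. Section 6.1.4.6 tracks subsequent therapy, response, progression-free survival and overall survival to 5 years, but not adverse events.

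**Step 2. Calendar**

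Inputs are the dosing days in Section 2.2 and the 28-day cycle. Study day = (cycle - 1) × 28 + day within cycle. Days are nominal, since dosing may move by 2 days either way.

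- Two cycles: last pembrolizumab and last chemotherapy are both on cycle 2 day 15, so (2 - 1) × 28 + 15 = 43.
- Six cycles: last pembrolizumab is cycle 6 day 8, so (6 - 1) × 28 + 8 = 148. Last chemotherapy is cycle 6 day 15, so (6 - 1) × 28 + 15 = 155.

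| | Two cycles | Six cycles |
|---|---|---|
| Last study drug | 43 | 155 |
| Routine window closes (+30) | 73 | 185 |
| Serious and clinical-interest window closes (+90) | 133 | 245 |
| Uncovered interval | 133 - 73 = 60 days | 245 - 185 = 60 days |
| Routine closure, counted from last pembrolizumab | 73 - 43 = 30 days | 185 - 148 = 37 days |

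**Step 3. Size**

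The number of missed events depends on how often non-serious immune events begin in the uncovered interval. The documents give no such rate. As an illustration only, assume a per-patient probability p of 2%, 5% or 10%. Among the 50 planned patients the chance of at least one such event is 1 - (1 - p)^50, which gives 64%, 92% and 99.5%. This shows that the gap need not be empty. It is not an estimate of the bias.

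**The case against.** The strongest reply is that the protocol does not leave late toxicity unrecorded, and much of it stands.

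- A reader might infer that late immune events are missed by design. Section 6.1.2.1 says otherwise. The documents hold two positions, so this is a conflict between sections, with the gap appearing in the operative ones.
- A reader might also infer that a Grade 3 immune event without hospitalisation, after day 30, is neither serious nor of clinical interest. That does not follow. Table 7 and Section 6.3.2 allow an event to be serious on medical judgement without hospitalisation, and some hepatic events meet the clinical-interest pattern. What remains is events judged not medically important, mainly of lower grade.
- It is tempting to say that if some share of immune events starts late, the reported rate is too low by that share. This would treat every late event as lost, although late serious and clinical-interest events are still reported.
- No listed objective is an immune-event rate. The Part A criterion is a delay of more than 3 weeks within two cycles, which Section 7.1 reports as met. The Part B endpoint is 1-year EFS. Neither uses this window.
- A longer window has limits of its own. Ninety days does not clearly span several months. Follow-up is standard of care with no scheduled laboratory tests after the safety visit, so detection would be uneven. Events arising after new anti-cancer therapy are hard to attribute.

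These points narrow the finding. None supplies a working route for the last row of the table in Step 1.

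**Conclusion.** The point holds in a limited form and is a cheap improvement. Sections 5.0, 6.1.4.5 and 6.2 stop recording new non-serious events, including the immune-related ones that Section 6.2 singles out, about 30 days after the last dose or at the start of other therapy. That is shorter than the latency stated in Section 4.2.2 and conflicts with Section 6.1.2.1.

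The measurable extent is 60 days of a 90-day window that the plan already keeps open for other events. After day 90 a new non-serious immune event has no operative route either. The effect on any reported rate cannot be quantified from the documents, and the illustration above rests wholly on assumed rates. The consequence is an incomplete description of late, mostly milder immune toxicity. The documents do not support extending this to the Part A safety conclusion or to the Part B efficacy result.

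**What to change.** Amend Sections 6.2 and 6.1.4.5 so that new immune-related adverse events of any grade are recorded through the window already used for serious and clinical-interest events: 90 days after treatment ends, or 30 days after it ends if new anti-cancer therapy starts. Keep the 30-day window for all other adverse events. Take the data from standard-of-care visits and records. Align Section 6.1.2.1, the Section 5.0 flow chart and its notes, and the concomitant-medication rule in Section 4.3.1 with this, so that all sections give one answer. Do not extend capture further once new therapy has begun, because the gain in completeness is offset by doubtful attribution.

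The cost is extra case report form entries and record review, with no added visit or test. Two limits should be stated in the report. Ascertainment after day 30 will reflect what standard care detects. Part B patients will also have a longer window than Part A patients who have already passed it (29 of 30 Part A patients were enrolled by May 2021), so late immune events should be reported by part and not pooled without comment.
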